
To evaluate the effect of EDP1815 on length of hospitalization and recovery in participants with COVID-19	
Time to discharge, defined as the time in days from start of treatment to first occurrence of a WHO OSCI score of 2 or less.Time to oxygen saturation (SpO_2) $\geq 94\%$ on room air without further requirement for oxygen therapy.Time to recovery, defined as the time in days from symptom onset to alleviation of all COVID-19 symptoms.

To evaluate the safety and tolerability of EDP1815 in participants with COVID-19	
Incidence and severity of treatment emergent adverse events and serious adverse events.Incidence of clinically significant abnormal changes in safety laboratory parameters.
Exploratory	

To evaluate the effect of EDP1815 on the exaggerated host cytokine response to COVID-19 infection	
Change from baseline in cytokine levels (including IL-6) at day 4 and day 7 (and/or at additional timepoints if samples are available).Change from baseline in inflammatory response at day 4 and day 7 (and/or at additional timepoints if samples are available).

To identify clinical or biochemical predictors of response to EDP1815, and to confirm lack of systemic absorption.	
Statistical significance of each potential predictor-treatment interaction in exploratory models based on the final selected model for the primary efficacy analysis.To identify the presence of EDP1815 in stool and/or blood using PCR primers

4. Study Design

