9.4.1.3. Exploratory Efficacy Analysis

Exploratory endpoints will be summarized.

Exploratory modelling will be performed to look for potential predictors of response. This will use the model for change from baseline in trough S/F ratio from the primary analysis, including any baseline covariates found to be significant. For each potential predictor, the variable and its interaction with treatment will be added to the base model from the primary analysis and look for significant interactions. If during the course of the study, a newly approved medication for COVID-19 becomes part of the standard of care treatment at the investigational site, the interaction between treatment and the covariate defined by use of the new medication will also be investigated as part of this exploratory analysis.

Full details will be provided in the SAP.

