 - New SOC covariate will be fitted as a time-dependent covariate with value 'yes' at time t if taken prior to time t, 'no' otherwise.

Note that the purpose of this sensitivity analysis is to account for any biases to the endpoints caused by a standard of care treatment that was available to later participants but not to those first entered. Any new medication that becomes standard of care and is available for use by all participants before Day 14 will not meet the criteria for performing this sensitivity analysis.

Subgroup analyses based on use of any new SOC medication may also be performed, depending on results seen from the sensitivity analyses using this covariate.

In addition to the covariates mentioned above, other baseline biomarkers will be examined for a prognostic effect on treatment response as part of the exploratory analysis. These will be fitted as continuous variables in the model and include the following:

- CRP (mg/dL)
- Neutrophils ($10^3/\mu\text{L}$)
- IL-6 (pg/mL)
- Ferritin (ng/mL)
- D-dimer (ng/mL)
- Neutrophil/Lymphocyte ratio (fraction of 1)
- Lactate Dehydrogenase (LDH) (IU/L)
- Troponin I (ng/mL)

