7.5 Multiple Testing

No adjustments for alpha spending will be performed.

8 Summary of Study Data

All continuous variables will be summarized using the following descriptive statistics: n (non-missing sample size), mean, SD, median, maximum and minimum. The frequency and percentages (based on the non-missing sample size) of observed levels will be reported for all categorical measures.

In general, all data will be listed, sorted by randomized treatment (Placebo, EDP1815) and participant number. If additional sites are added, then data will be sorted by participant number within site. Relevant listings will include whether the assessment was performed and the date, study day/visit and time of the assessment as applicable.

Unless otherwise specified below, all summary tables will be structured with a column for each treatment (placebo, EDP1815) and, for data collected prior to dosing, will include an overall total column where appropriate.

Columns will be ordered and labelled as follows:

- Placebo
- EDP1815
- Total

Except for disposition tables in which it is appropriate to include screened subjects, the enrolled population will be used, otherwise the ITT population will be used for all summaries of disposition, demographic and baseline data and efficacy.

The safety population will be used for all summaries of safety.

Unless otherwise specified, all listings will be produced using the ITT population.

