9.4 Exploratory Efficacy Analyses

9.4.1 Biomarkers

[Table 16](#) shows the parameters which will be collected and the units in which they will be supplied.

Actual values and change from baseline in cytokine levels will be summarized at Days 4 and 7. All cytokine level data will also be listed.

Actual values and change from baseline in inflammatory response markers will be summarized at Days 4 and 7. All inflammatory response marker data will also be listed.

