14.2.3.2.3	Analysis of Percentage Change from Baseline in S/F Ratio at Days 4, 7, 10 and 14, Sensitivity Analysis Using MMRM approach	ITT		Only produced if >10% drop-out before D14
14.2.3.2.4	Analysis of Percentage Change from Baseline in S/F ratio at Days 4, 7, 10 and 14, Sensitivity Analysis Accounting for Use of New SOC	ITT		Only produced if a new SOC is introduced during the study
14.2.4.1	Summary and Analysis of WHO OSCI score at Days 4, 7, 14, 21 and 42	ITT	Yes, summary only	DMC-Unblinded
14.2.4.2	Shift Table of Changes from Baseline in WHO OSCI Score at Days 4, 7, 14, 21 and 42	ITT	Yes	DMC-Unblinded
14.2.4.3	Summary of Participants Remaining at or Below Their Baseline WHO OSCI Scale Score at Days 4, 7, 14, 21 and 42	ITT	Yes	DMC-Efficacy
14.2.4.4	Summary and Analysis of Maximum WHO OSCI Score Reported	ITT	Yes, exclude p-value	DMC-Efficacy
14.2.5.1	Summary and Analysis of Overall Survival	ITT	Yes, exclude Hazard ratio, CI and p-value	DMC-Efficacy
14.2.5.2	Summary and Analysis of Overall Survival, Sensitivity Analysis Accounting for Use of New SOC	ITT		
14.2.6.1	Summary and Analysis of Intubation and Mechanical Ventilation Free Survival	ITT	Yes, exclude Hazard ratio, CI and p-value	DMC-Efficacy

Number	Title	Population	Early Stop	Programming notes ¹
14.2.6.2	Summary and Analysis of Intubation and Mechanical Ventilation Free Survival, Sensitivity Analysis Accounting for Use of New SOC	ITT		
14.2.7	Summary and Analysis of Time to Discharge	ITT	Yes, exclude Hazard ratio, CI and p-value	DMC-Efficacy
14.2.8	Summary and Analysis of Time to SpO ₂ ≥94% on Room Air Without Further Requirement for Oxygen Therapy	ITT	Yes, exclude Hazard ratio, CI and p-value	DMC-Efficacy
14.2.9	Summary and Analysis of Time to Recovery from Onset of Symptoms	ITT	Yes, exclude Hazard ratio, CI and p-value	DMC-Efficacy
14.2.10	Summary of Number of Days Requiring Oxygen Therapy	ITT	Yes	DMC-Efficacy
14.2.11	Summary of Number of Days with Pyrexia	ITT	Yes	DMC-Efficacy
14.2.12	Summary of Maximum Daily Temperature	ITT	Yes	DMC-Efficacy
14.2.13	Summary of Maximum and Minimum Daily SpO ₂ values	ITT	Yes	DMC-Efficacy
14.2.14	Summary of Change from Baseline in Cytokine levels at Days 4 and 7	ITT		
14.2.15	Summary of Change from baseline in Inflammatory Response Markers at Days 4 and 7	ITT	Yes	
14.2.16	Exploratory Analysis of Potential Predictor-Treatment Interactions	ITT		

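### SAP 9.4.1 gives the cytokine and inflammatory-marker objective per-arm summaries but no treatment effect estimate; a log-scale, baseline-adjusted comparison of a few lead markers would supply one

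*SAP*

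**What the plan says.** The exploratory objective in Protocol section 3 (repeated in SAP Table 1) is worded as a treatment effect: "To evaluate the effect of EDP1815 on the exaggerated host cytokine response to COVID-19 infection".

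The planned analysis is descriptive throughout:

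- Protocol 9.4.1.3: "Exploratory endpoints will be summarized".
- SAP 9.4.1, cytokines: "Actual values and change from baseline in cytokine levels will be summarized at Days 4 and 7".
- SAP 9.4.1, other markers: "Actual values and change from baseline in inflammatory response markers will be summarized at Days 4 and 7".
- SAP section 8: "All continuous variables will be summarized using the following descriptive statistics: n (non-missing sample size), mean, SD, median, maximum and minimum".
- SAP 16.2.1, output 14.2.14: "Summary of Change from Baseline in Cytokine levels at Days 4 and 7". Output 14.2.15, for inflammatory markers, is also titled as a summary, whereas the S/F ratio outcomes have separate analysis tables.

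SAP 5.3.3.9 sets cytokine results beyond an assay limit to the limit. The only log-transformation in the SAP (9.1.1.2) concerns the response variable of the efficacy models.

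For the second exploratory objective, SAP 7.2 lists eight baseline biomarkers (CRP, neutrophils, IL-6, ferritin, D-dimer, neutrophil/lymphocyte ratio, LDH, troponin I) in native units and says "These will be fitted as continuous variables in the model and include the following". SAP 9.4.2 reports one interaction p-value per predictor.

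**The concern.** The protocol's rationale is that EDP1815 lowers IL-6, IL-8 and TNF-alpha, and the pilot is meant to judge endpoints for sensitivity and inform later sample sizes. Two columns of summary statistics give neither an effect size with its uncertainty nor a log-scale SD for planning. The baseline sample is used only by subtraction.

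If the markers are right-skewed and change by ratios, a few participants with very high baselines dominate the mean and SD of the raw change. The same participants would dominate an interaction slope fitted to an untransformed predictor. The samples are already being taken, so at stake is how much the pilot learns about mechanism from them.

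**Working it through.** **The plan's own precision figure.** The only one is SAP Table 8, for trough S/F ratio: half-width = t(0.975, N−2) × SD × √(4/N). For N = 60 and SD 100 this is 2.002 × 100 × 0.2582 = 51.7, as stated; all 18 cells reproduce. There is no biomarker counterpart, so what follows rests on assumed variability.

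**Baseline adjustment alone.** Take equal SD at baseline and follow-up, with correlation r. In units of that variance, the arm difference has variance proportional to 2(1−r) for a change score and 1−r² for ANCOVA, a ratio of (1+r)/2. At r = 0.5 this is 0.75, so the half-width is √0.75 = 0.87 of the change-score width. At r = 0.3 and 0.7 the factors are 0.81 and 0.92. Adjustment alone is therefore a moderate gain, 8–19% narrower.

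**Adding the log scale.** Simulation inputs: 30 per arm (60 participants 1:1, Protocol 9.1); log-normal marker; true EDP1815/placebo ratio 0.5; no placebo change; two-sided 5%. Log-SD and r are assumptions. Power at r = 0.5, from 2,000 trials per cell:

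| Log-SD | Raw change | Raw ANCOVA | Log change | Log ANCOVA | 95% CI factor, log ANCOVA |
|---|---|---|---|---|---|
| 0.7 | 0.74 | 0.96 | 0.97 | 0.99 | 1.37 |
| 1.0 | 0.36 | 0.64 | 0.77 | 0.85 | 1.56 |
| 1.3 | 0.20 | 0.37 | 0.54 | 0.65 | 1.79 |

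The last column is exp[t(0.975, 57) × log-SD × √(1−r²) × √(4/60)]. At log-SD 1.0 this is exp(2.002 × 1.0 × 0.866 × 0.2582) = exp(0.448) = 1.56, so an estimated ratio of 0.50 would carry an interval of 0.32 to 0.78. With no true effect, each method rejected in about 3–6% of trials.

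Over log-SD 0.8–1.3 and r 0.4–0.6, raw-change power is about 52–67%, 32–41% and 17–20% at log-SD 0.8, 1.0 and 1.3. Raw ANCOVA spans about 31–91% and log ANCOVA about 58–99%. If markers also fall 30–40% in both arms, raw-change power drops to about 10–41%; log ANCOVA is unchanged, because a common fall only moves the intercept.

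With 26 per arm (the 13% drop-out row of Table 8) and r = 0.5, raw change against log ANCOVA is 0.69 against 0.98, 0.32 against 0.80 and 0.17 against 0.58 at log-SD 0.7, 1.0 and 1.3. Missing Day 4 or Day 7 samples act in the same direction.

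**Predictors.** For 60 values of a log-normal predictor, the single most extreme participant supplies a median of 25%, 34% and 42% of the sum of squares on the raw scale at log-SD 0.7, 1.0 and 1.3. On the log scale the figure is 11%.

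**Number of contrasts.** SAP Table 16 lists 40 cytokines and 5 inflammatory markers. At two days that is 45 × 2 = 90 intervals, of which 90 × 0.05 = 4.5 would exclude 1 by chance. Six lead markers give 12 intervals and 0.6.

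**The case against.** The best reply is that this is an exploratory objective in a pilot without a power calculation, that the SAP follows Protocol 9.4.1.3, and that SAP section 9 calls every analysis descriptive. No primary, secondary or safety conclusion depends on it, and the data remain available for later work. All of that stands, and it limits the weight of the point. It does not explain the gap: under the same descriptive label, the primary endpoint gets a baseline-adjusted difference with 95% CI (SAP 9.2.2) and the other exploratory objective gets fitted models (SAP 9.4.2).

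It is also fair that the plan contains no test of raw change, so the raw-change column is the weakest comparison a reader might make from the tables, not the planned analysis. Actual values and medians are tabulated by arm and all data are listed; medians resist outliers. They still come without an arm difference or interval.

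Modelling every marker would produce many unadjusted intervals, and values set to an assay limit can distort a log-scale model. Both objections stand and shape the fix.

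A reader might also infer that multi-site local laboratories put scale differences into the raw changes. The documents do not establish this. SAP 10.4 specifies local data for safety laboratory tests only, nothing says where the cytokine panel is assayed, and Table 16 fixes one unit per inflammatory marker. Each site also receives complete randomization blocks (SAP 5.2), so such a difference would mainly add noise.

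**Conclusion.** The concern holds as a missed, inexpensive improvement. For cytokines and inflammatory markers the plan has no treatment contrast, baseline adjustment or log scale, so its stated effect objective is left without an estimate.

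Under the assumptions given (log-normal markers, 30 per arm, a halving, log-SD 0.8–1.3, r 0.4–0.6, flat placebo), log-scale ANCOVA has about 58–99% power against 17–67% for raw changes. Raw-scale ANCOVA closes only part of that gap, so both the adjustment and the scale matter. None of these variances comes from the documents.

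Two stronger readings should be resisted. One is that a real halving would generally be lost in noise: at log-SD 0.8 with a flat placebo arm, even raw changes detect it more often than not. The other is that SAP 7.2 commits to raw-scale predictors. It lists native units but is silent on transformation, and CRP and neutrophils also enter as cut-offs. The predictor point is a request to state the scale, supported by the 25–42% against 11% calculation.

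**What to change.** In SAP 9.4.1, keep the raw summaries and name a short list of lead markers, for example IL-6, IL-8 and TNF-alpha from the rationale, plus CRP, ferritin and D-dimer. TNF-alpha depends on being assayed: Protocol 8.5.2 treats it as optional, although SAP Table 16 lists it. At Day 4 and Day 7, fit log(value) on treatment and log(baseline). Report the EDP1815/placebo geometric mean ratio with 95% CI, labelled exploratory, and show for each marker and day how many values were set to an assay limit.

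In SAP 7.2 and 9.4.2, state that the skewed continuous biomarker predictors enter on the log scale.

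The cost is one SAP paragraph, one sentence on predictors and one extra table. No samples or visits are added. The downside is a few more unadjusted intervals, which SAP section 9 already treats as descriptive.

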9.4.2 Potential Predictors of Response to EDP1815

To identify clinical and biochemical predictors of response to EDP1815 exploratory modelling will be performed to identify potential interactions between treatment and each covariate defined in [Section 7.2](#). The model fitted for the primary analysis of change from baseline in trough S/F ratio will be considered as the base model for this. For each potential predictor, the covariate (if not already fitted) and the treatment-covariate interaction will be added to the base model and the p-value for the treatment-covariate interaction will be reported. Each potential predictor will be considered in a separate model independently of other potential predictors.

In the event that a predictor is found to have a significant treatment interaction with EDP1815 on the primary endpoint, further exploratory analyses will be performed to find the extent and direction of the interaction as well as looking at the effect on other secondary endpoints. Any such analyses will be considered as adhoc and will not be further described here.

10 Safety Analyses

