
To evaluate the effect of EDP1815 on the exaggerated host cytokine response to COVID-19 infection	
Change from baseline in cytokine levels (including IL-6) at day 4 and day 7 (and/or at additional timepoints if samples are available).Change from baseline in inflammatory response at day 4 and day 7 (and/or at additional timepoints if samples are available).

To identify clinical or biochemical predictors of response to EDP1815.	
Statistical significance of each potential predictor-treatment interaction in exploratory models based on the final selected model for the primary efficacy analysis.To identify the presence of EDP1815 in stool and/or blood using PCR primers

5 Study Methods

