7.2 Covariates and Subgroups

The following covariates will be considered as possible prognostic factors for inclusion in the analysis models described in [Section 7.2](#):

- Age ≥ 60 years (yes, no)
- Gender (male, female)
- Race (Non-Hispanic/Latino white, non-white or Hispanic/Latino)
- Baseline WHO OSCI score (4, 5)
- Time since onset of symptom at Baseline (days)
- Presence of obesity: BMI $\geq 30 \text{ kg/m}^2$ (yes, no)
- Current type 1 diabetes (yes, no)
- Current type 2 diabetes (yes, no)
- Current hypertension (yes, no)
- Other current chronic cardiovascular disease (yes, no)
- Current chronic respiratory disease (yes, no)
- Active cancer, excluding skin basal cell carcinoma or localized squamous cell carcinoma (yes, no)
- Smoking status (current smoker, not current smoker)
- Neutrophils $> 8.0 \times 10^3/\mu\text{L}$
- C-Reactive protein (CRP) $> 40 \text{ mg/dL}$

Other covariates may also be considered if emerging research into COVID-19 suggests other possible prognostic factors for outcome that can be determined from the data captured on the CRF.

Prior to database lock, the inferential primary analysis model described in [Section 9.2.2](#) will be examined on the blinded data in order to determine which baseline factors may have a prognostic effect on the efficacy endpoints. Covariates will be selected for inclusion in the model using forward stepwise selection procedure with a 5% level of significance applied for both the selection and deselection of variables from the model.

Where applicable, the baseline value of the endpoint will be automatically fitted first, regardless of significance before additional covariates are considered. A maximum of 3 covariates, in addition to the

baseline value where applicable, may be selected for each model in order to avoid over-parameterization and a reduction in the efficiency of treatment estimates.

If, during the study, a new treatment is approved for use in COVID-19 and becomes part of the standard of care for hospitalized participants at the study site(s), additional sensitivity analyses will be performed using covariates defined by use of this treatment.

- For ANCOVA analyses of trough S/F ratio
 - New SOC covariate: 'yes' if taken at any time before Day 14, 'no' otherwise
- For ANOVA analyses of S/F ratio at Day X
 - New SOC covariate: 'yes' if taken prior to Day X, 'no' otherwise
- For time-to-event analyses

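### The predictor search (SAP 9.4.2) specifies a p-value for every interaction, but looks at size and direction only when the interaction is significant

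*SAP*

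**What the plan says.** SAP 9.4.2 takes the primary ANCOVA for change from baseline in trough S/F ratio as its base model and states that "exploratory modelling will be performed to identify potential interactions between treatment and each covariate defined in" Section 7.2. Each predictor gets its own model, and the output named for each is that "the p-value for the treatment-covariate interaction will be reported".

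The next step is conditional: "In the event that a predictor is found to have a significant treatment interaction with EDP1815 on the primary endpoint", further work will establish how large the interaction is, which way it goes, and how it bears on secondary endpoints. That work is called ad hoc and is not described. SAP 9.4.2 gives no significance level.

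SAP 7.2 supplies the predictors. One list opens "The following covariates will be considered as possible prognostic factors for inclusion in the analysis models described in" and has 15 entries. A second says "other baseline biomarkers will be examined for a prognostic effect on treatment response as part of the exploratory analysis" and has 8 continuous biomarkers. CRP and neutrophils are in both, dichotomized and continuous. The list may grow: "Other covariates may also be considered if emerging research into COVID-19 suggests other possible prognostic factors".

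The endpoint in SAP Table 1 (and in Tables 1 and 2 of the protocol) is itself framed as significance: "Statistical significance of each potential predictor-treatment interaction in exploratory models". Protocol 9.4.1.3 describes the same search for significant interactions. SAP 9 calls all analyses descriptive, without multiplicity adjustment.

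**The concern.** Under this plan, the p-value decides whether anyone looks at an effect size. With 60 participants an interaction must be estimated as very large to be significant, so the estimates that get examined are, on average, too large. Some will come from predictors with no effect at all. For the remaining predictors, a p-value alone shows neither direction nor precision. A reader cannot tell a predictor with a small interaction from one about which the trial says almost nothing.

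What is at stake is the usefulness of an exploratory objective: identifying clinical or biochemical predictors of response. No confirmatory conclusion depends on it.

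**Working it through.** **Reproducing the plan's own figure.** SAP Table 8 gives 95% CI half-widths for the treatment difference. The formula is t(0.975, N−2) × SD × √(4/N). With SD 100 this gives 51.68 at N = 60 and 39.69 at N = 100; the table prints 51.7 and 39.7. All 18 entries reproduce. The SAP gives no error rate or power for the predictor search.

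**Inputs from the documents.** 15 + 8 = 23 predictors (SAP 7.2); 60 participants at 1:1, possibly 100 (SAP 5.1); SD scenarios of 50, 100 and 150 (SAP Table 8).

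**Assumptions.** A two-sided 5% level, borrowed from covariate selection (SAP 7.2) and the new-medication interaction (SAP 9.2.4). Binary predictors split 50/50 or 30/70. True interactions of 0.3, 0.5 and 0.8 residual SD.

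**False positives if no predictor is real**
- Expected number: 23 × 0.05 = 1.15.
- Chance of at least one, independent tests: 1 − 0.95^23 = 69%.
- With 21 effective tests, 66%; with 15, 54%; with 12, 46%.
- Simulation (2,000 null trials per setting; N = 60 and 100; assumed prevalences; latent correlation 0 to 0.5; CRP and neutrophils entered twice; non-estimable models dropped): chance of at least one 54–68%, mean number 1.05–1.20.

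**Precision of a binary-predictor interaction**
- SE in residual SDs, with prevalence p: (2/√N) / √(p(1−p)).
- N = 60: 0.258/0.5 = 0.516 (50/50) and 0.258/0.458 = 0.563 (30/70).
- N = 100: 0.400 and 0.436.
- Smallest significant estimate at N = 60, with t(0.975, 55) = 2.004: 1.03 SD (50/50) and 1.13 SD (30/70).
- If the residual SD is 100, the 50/50 threshold is 2.004 × 51.6 ≈ 103 S/F units. That is twice the 51.7 half-width for the overall treatment difference.

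**Power and average exaggeration.** The estimate is taken as normal around the truth, with the residual SD estimated on N − 5 degrees of freedom. Exaggeration is the mean absolute estimate, given significance, divided by the truth. Each cell shows the 50/50 split, then 30/70.

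| True interaction (SD) | Power, N = 60 | Exaggeration, N = 60 | Power, N = 100 | Exaggeration, N = 100 |
|---|---|---|---|---|
| 0.3 | 9%, 8% | 4.1, 4.5 | 11%, 10% | 3.2, 3.5 |
| 0.5 | 16%, 14% | 2.5, 2.8 | 24%, 20% | 2.0, 2.2 |
| 0.8 | 33%, 29% | 1.7, 1.8 | 51%, 44% | 1.4, 1.5 |

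Treating the residual SD as known moves the largest ratio from 4.5 to 4.6, hence the upper figure of 4.6.

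**Comparison within the SAP.** For the new-medication interaction, SAP 9.2.3 provides LS means for each group and their difference in addition to the interaction p-value. The predictor search specifies no such estimates.

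**The case against.** The strongest reply is that the plan hides nothing. The search is labelled exploratory, its follow-up ad hoc, and all analyses descriptive and unadjusted. A screen of 23 covariates will produce false leads, and their expected number can be worked out from the published list. This stands. A reader might infer a failure of multiplicity control, but the documents make no claim that would need it.

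Other strong readings also go beyond the text:
- **Only p-values will ever be shown.** The SAP does not say this. It specifies no estimate, and Table 14.2.16 appears by title alone. SAP 12 has general formatting rules for regression coefficients and intervals, but they do not commit this table to showing any.
- **Non-significant predictors are discarded.** Their p-values are still reported.
- **The search is meant to choose predictors for a later trial.** The stated use for future studies is evaluating endpoints and informing sample size.
- **Exaggeration is certain.** Selection inflates estimates on average at low power. It does not determine any single estimate.

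The figures also have limits. The 69% assumes independent tests; the duplicated CRP and neutrophil terms and the neutrophil/lymphocyte ratio overlap. Chronic respiratory disease is a listed predictor although significant chronic respiratory disease is an exclusion, so that model may not be estimable. Nine of the 23 predictors are continuous (time since symptom onset and the eight biomarkers), and the power table does not cover them. If the study stops early for low recruitment, SAP 9.1.1.1 drops inferential efficacy analysis and the search would not run.

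None of this answers the narrower point: a p-value that decides whether an effect is estimated is a poor descriptive output.

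**Conclusion.** The point holds as a minor, inexpensive improvement. SAP 9.4.2 makes estimation conditional on significance in tests with little power. If no predictor is real, about 1.1 false positives are expected, with roughly a 54–69% chance of at least one. That chance falls below one half only if about 13 or fewer effective tests remain (1 − 0.95^13 = 49%). For binary predictors, power is about 8–33% at N = 60 and 10–51% at N = 100. Significant estimates average about 1.7–4.6 and 1.4–3.5 times the truth respectively.

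These figures rest on the inferred 5% level, the assumed prevalences and the assumed true interactions. The case for reporting every estimate does not depend on their exact size.

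**What to change.** In SAP 9.4.2 and Table 14.2.16, report for every predictor, whatever its p-value, the interaction estimate with its 95% CI. For binary predictors, add the treatment difference with 95% CI in each level, and mark levels where it cannot be estimated.

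Reword the endpoint in SAP Table 1 so that it covers the size and precision of each interaction and is not defined by statistical significance alone. The protocol carries the same wording, so record the change in SAP 14 or align the protocol.

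Two further changes are optional: entering CRP and neutrophils once each, and footnoting the number of tests with the expected number of false positives. The dichotomized forms are pre-specified risk factors, so keeping both is defensible.

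The cost is a few extra table columns. The interaction estimates come from models already being fitted, the level-specific differences can be derived from the same fits, and no new data are needed.
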